Baseline measures of effective renal plasma flow (ERPF), glomerular filtration rate (GFR), AKI biomarkers, plasma creatinine and renoregulatory hormones are obtained prior to surgery. Participants are randomised to the Low (0.2 ml/kg/h) or High (0.5 ml/kg/h) groups on induction of general anaesthesia. Randomisation is stratified by baseline renal function. Surgical techniques are per surgeon preference. Perioperative care is standardised according to the North Shore Hospital (NSH) enhanced-recovery after surgery (ERAS) protocol to minimise variation in ancillary care. This includes routine usage of epidural analgesia, routine urinary catheterisation until morning of postoperative day (POD) 2 and a standardised perioperative fluid protocol (see Table 1). During surgery and the next 48 hours, UO is monitored hourly. In both groups, an hourly UO <0.5 ml/kg/h prompts immediate anaesthetic or surgical team review to rule out evidence of potential hypoperfusion of any aetiology (see Figure 1). If this is not present, patients in the High group will receive 500-ml fluid boluses (Plasma-Lyte 148) until UO exceeds 0.5 ml/kg/h. In the Low group, fluid boluses will be only given if UO falls below 0.2 ml/kg/h.

The main endpoint is the urinary NGAL on POD 1. Neutrophil gelatinase-associated lipoprotein, the best-validated and most sensitive biomarker of AKI, will be followed 12-hourly during 48 hours. In addition, plasma cystatin C and creatinine concentrations, urinary electrolytes and osmolality will be measured several times per day, and the ERPF and GFR measurements will be repeated on POD 1. Renoregulatory hormones will also be followed. The study nephrologist will acutely assess any participant with a persistently

Table 2. Exclusion criteria
Preexisting moderate or severe chronic kidney disease (eGFR <60 ml/min/1.73 m ²)
Pre-existing kidney damage regardless of eGFR (single functional kidney, renal transplant, significant proteinuria)
History of previous AKI due to any cause (AKI Network Stage 2)
Need for ongoing angiotensin-converting enzyme inhibitors, angiotensin receptor blockers or non-steroidal anti-inflammatory drugs (NSAIDs)
Nephrotoxic substance administration (including systemic radiocontrast dyes, aminoglycosides, glycopeptides and NSAIDs other than aspirin) within 48 h prior to surgery
Pre-existing hepatic failure (Child-Pugh Score >6)
ASA class IV
Morbid obesity (BMI>35)
Intraoperative ureteric injury

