Urinary output is followed hourly. All anaesthetic and surgical teams providing care for participants will be educated face-to-face about the details of the fluid protocols. A research fellow will monitor compliance with protocols around the clock in person and over the phone.

Participants with epidural-related hypotension will follow the standard ERAS protocol (a combination of fluid boluses and reduced epidural infusion rates).

Participants with complications remain in the study. As per the study fluid algorithms (Figure 1), the UO target in the Low group will switch from 0.2 to 0.5 ml/kg/h if there are any signs of hypoperfusion.

At the routine 30-day outpatients clinic followup, a final urine and plasma sample will be collected.

Nephrologist review triggers: The on-site study nephrologist [name] (or a named colleague in his absence) will urgently (within 12 hours) review any participant with an absent UO response to a 2L fluid bolus (see Figure 2), or with AKI Network (AKIN) stage 2 AKI per creatinine criteria (persistent elevations of plasma creatinine $\geq 100\%$ above baseline despite adequate fluid resuscitation) within 30 days, and institute adequate therapy.

Independent Monitoring Committee: Two independent senior consultant nephrologists ([name] at Auckland City Hospital and [name] at Middlemore Hospital) make up an independent Monitoring Committee, which will review individual clinical outcomes as well as postoperative changes in plasma creatinine in all participants after completion of four and 20 participants.

Study halt triggers: In addition, the study will be halted pending urgent review by the independent Monitoring Committee if the following occurs: Two or more participants in the intervention arm develop AKI Network (AKIN) stage 3 AKI per creatinine criteria (persistent elevations of plasma creatinine $\geq 200\%$ above baseline despite adequate fluid resuscitation) within seven days after surgery and in the absence of a clear-cut alternative cause (such as major systemic complication of surgery).

Table 3. Secondary endpoints
Urinary excretion of NGAL 0800 POD1 - 0800 POD 2 and total excretion during intervention period
Urinary concentrations of NGAL and creatinine and osmolality during and after surgery
Plasma concentrations of cystatin C, creatinine, ADH, aldosterone, renin and angiotensin II and osmolality during and after surgery
ERPF and GFR before and 1 day after surgery

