30-day incidence of complications (including AKI) classified and defined as per Auckland ERAS database, graded per Clavien-Dindo grading scale
Length of stay, time to repeated flatus
IV and oral fluid volumes and changes in body weight and lean tissue mass (BIA)

Depending on the findings of the independent Monitoring Committee, the study may then close or resume with changes as recommended.

Endpoints

The primary endpoint is urinary concentration of NGAL at 2 pm on POD 1. Secondary endpoints are listed in Table 3.

Urine samples are collected once at the preoperative research visit and at regular intervals during and 72 hours after surgery and once on POD 30 (See further Blood and urine sampling protocol).

Plasma samples are collected three times at the preoperative research visit, at regular intervals during and 72 hours after surgery and once on POD 30. In addition, two more samples are taken when the sinistrin-PAH test is repeated 0800-1100 on POD 1 (See further Blood and urine sampling protocol).

Clinical data including demographics, diagnosis, surgery, anaesthesia, complications and recovery parameters are prospectively collected as per standard practice by an ERAS Nurse Specialist in the Auckland ERAS database.

Sample handling and analysis

A research fellow or a research nurse will collect all samples. Some assays will be performed on collection by Waitemata DHB Laboratories; others will be stored in a dedicated -80°C alarmed research freezer at Waitemata DHB Laboratories for later batch analyses by the Christchurch co-investigators. All assays will be performed by staff unaware of participants' group allocation.

Statistical considerations

On the basis of a recent study in surgical trauma, the mean (SD) urinary NGAL concentration at 2pm on the first postoperative day in the control (High) group is assumed to be 10 (10) ng/ml, and the clinically significant cut-off in the Low group is assumed to be 25 ng/ml. To show non-inferiority with 90% power, a minimum of 18 participants completing the study per treatment group will be needed based on a margin of non-inferiority of 15 µg/L (25-10 ng/ml), a common SD of 15 ng/ml, and 0.05 one-sided significance level. Assuming 10% dropout, 20 participants per treatment group will be recruited (40 participants in total).

Certain data indicate that urinary NGAL follows a log-normal distribution. To ensure this will not increase the sample size required, a sample size calculation taking this into account

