has also been performed. This indicates that a minimum of 31 participants, 15.3 in each treatment arm, will be needed based on a margin of non-inferiority of log 15 ng/ml and an SD of log 10 ng/ml, with 90% power using a one-sided statistical test with an alpha level of 0.05. A sample size of 40 patients will therefore be sufficient should urinary NGAL be log-normally distributed in the planned study. This sample size calculation was performed with the assistance of [name], Waitemata DHB statistician.

Repeated measures will be analysed by analyses of variance for repeated measures (time x treatment group with post-hoc Tukey's test as appropriate) or mixed regression models if appropriate. Student's unpaired t-test or, if non-normally distributed, Mann-Whitney U test and Fisher's exact test will be used as appropriate.

Planned subgroup analysis are: moderate vs no chronic kidney disease, patients with vs without epidural analgesia, patients undergoing surgery via laparotomy vs laparoscopy.

Appendices

1. Blood and urine sampling protocol
2. Clearance studies protocol

References

Sweny P. Is postoperative oliguria avoidable? *Br J Anaesth*. 1991;67:137-145.

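### Serial urinary NGAL: repeated-measures ANOVA is named first, with no log scale and no rule for taking the mixed-model alternative, which costs sensitivity to a Low-arm rise in secondary endpoints

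*Protocol*

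**What the plan says.** Under Statistical considerations, the protocol states "Repeated measures will be analysed by analyses of variance for repeated measures", testing time x treatment group with Tukey comparisons, "or mixed regression models if appropriate". It gives no rule for choosing between the two. No transformation is named for the serial data, and none is excluded.

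Non-normality is provided for in the next sentence, but only for the two-group comparison: "Student's unpaired t-test or, if non-normally distributed, Mann-Whitney U test".

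On the distribution of NGAL, the same section says "Certain data indicate that urinary NGAL follows a log-normal distribution". It assumes a control mean (SD) of 10 (10) ng/ml and adds a log-scale calculation to show that 40 patients suffice "should urinary NGAL be log-normally distributed in the planned study".

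Under Study design, NGAL "will be followed 12-hourly during 48 hours". Table 3 lists the serial values as secondary: "Urinary concentrations of NGAL and creatinine and osmolality during and after surgery". The primary endpoint is a single value: "The primary endpoint is urinary concentration of NGAL at 2 pm on POD 1".

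**The concern.** For a concentration that cannot be negative, an SD equal to the mean implies marked right skew. The authors took this seriously enough to check the sample size on the log scale, and they gave the two-group test a rank-based alternative. Neither precaution is carried into the serial analysis, where the method named first assumes similar variance across arms and times.

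If NGAL behaves as the planning figures suggest, that assumption fails where a harmful rise would appear. Doubling a mean (SD) of 10 (10) gives 20 (20), so the variance goes from 100 to 400 on the raw scale. On the log scale the same doubling is a shift of ln 2 = 0.69 with unchanged variance.

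Classical repeated-measures ANOVA also uses only participants with a complete set of samples.

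The Aims section relies on frequent biomarker sampling to pick up even slight renal harm, and the serial profiles are where a rise away from 2 pm on POD 1 would show. In a trial that hopes to find no harm, a less sensitive analysis of those profiles leans towards the hoped-for reading.

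**Working it through.** **The plan's own figure.** Raw-scale non-inferiority, margin 15, SD 15, one-sided 0.05, 90% power: n per arm = 2 x (1.645 + 1.282)² x (15/15)² = 17.1, so 18, and 18/0.90 = 20 recruited. The stated 18 and 20 are reproduced (exact t-test power at 18 per arm is 90.2%). The log-scale inputs, margin log 15 and SD log 10, give 12.4 per arm at one-sided 0.05. The stated 15.3 is close to the 15.2 obtained at one-sided 0.025. That gap is conservative and does not bear on this point.

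**Inputs from the protocol.** Mean (SD) 10 (10), so log SD = √ln(1 + (10/10)²) = √0.693 = 0.83. There are 18 completers or 20 recruited per arm. Sampling 12-hourly over 48 hours gives about five serial samples (0, 12, 24, 36 and 48 h), or six with baseline.

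**Assumptions, not in the protocol.** Within-patient correlation is 0.5 (0.7 as a variant), missed samples are 0% to 10% each and at random, NGAL is log-normal, and the rise is multiplicative. The sampling appendix is not in the text at hand. The Endpoints section also mentions 72 hours and POD 30, so the number of samples is itself an assumption.

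**Time x treatment test.** Simulation with 18 per arm, baseline plus five postoperative times, correlation 0.5, no missed samples, two-sided 0.05 (Greenhouse-Geisser corrected in brackets):

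| Low-arm NGAL | Raw | Log |
|---|---|---|
| Doubled at all five times | 42% (29%) | 67% (64%) |
| Doubled at two of five times | 82% (70%) | 89% (88%) |

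With no true difference, every version rejects in about 5% of runs or fewer, so the log-scale gain is not bought with false positives. At 4,000 runs the simulation error is √(0.42 x 0.58/4000), about 0.8 points.

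**Overall group test.** In the same 18-per-arm setting with a sustained doubling, raw is about 6 to 7 points below log. A separate simulation used 20 per arm, five serial samples without baseline and 1,500 runs per cell. Power for a sustained doubling at correlation 0.5 / 0.7 was:

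| Missed per sample | ANOVA, raw, complete cases | All available samples, raw | All available samples, log |
|---|---|---|---|
| 0% | 82% / 71% | 82% / 71% | 90% / 83% |
| 5% | 71% / 61% | 84% / 74% | 90% / 85% |
| 10% | 58% / 46% | 84% / 72% | 91% / 82% |

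The scale alone costs 90 - 82 = 8 points or 83 - 71 = 12 points with no missed samples. Dropping incomplete participants costs a further 84 - 71 = 13 points at 5% missed and 84 - 58 = 26 points at 10% (correlation 0.5). Using all available samples, even untransformed, recovers that second loss.

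**Participants dropped by ANOVA.** With six samples, the fraction with at least one missed is 1 - (1 - p)⁶. At p = 0.02 it is 1 - 0.886 = 11%, leaving about 35 of 40. At p = 0.05 it is 1 - 0.735 = 26%, leaving about 29 of 40.

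**The case against.** The strongest reply is that the same sentence already permits mixed models, so nothing commits the trial to discarding incomplete participants. Transformation, model choice and missing samples are also commonly settled in an analysis plan, which may exist here. Much of this stands. A reader might infer that loss of participants is built into the protocol; it is not, and the table shows that the permitted alternative removes it. What remains is that the text sets an order of preference without a criterion, and provides for non-normality in one test but not in the other, after raising log-normality for the very marker concerned.

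A reader might also infer that the protocol declares NGAL log-normal, or that all the renal markers are skewed. The wording is hedged and conditional, and it concerns urinary NGAL only. Nothing is said about the distribution of cystatin C, creatinine, osmolality or the hormones.

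Nor do the documents support the idea that dropped participants would be the sicker ones. Participants with complications stay in the study, research staff collect all samples, and catheters stay in until POD 2.

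Finally, the size depends on the test. The 25-point gap (67 - 42) belongs to the time x treatment interaction. For a sustained rise, the group effect from the same ANOVA is a natural test, and there the gap is much smaller.

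**Conclusion.** The point holds in a limited form. The protocol puts first, for serial urinary NGAL, a method ill suited to the skew that its own planning figures imply. It gives neither a scale nor a rule for taking the better alternative.

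If the analysis were run untransformed, power to see a sustained doubling would fall from about 67% to 42% on the time x treatment test and by about 6 to 12 points on the group test. If ANOVA were chosen as well, a further 11% to 26% of participants might be lost. These figures rest on log-normal data, a multiplicative rise, a correlation of 0.5 to 0.7, five or six samples and the assumed rates of missed samples. If NGAL proves nearly symmetric, the gain from the log scale shrinks.

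It would be tempting to conclude that the non-inferiority result itself is compromised. It is not: the primary comparison uses one time point and does not pass through this analysis, and the protocol nowhere says that a non-significant serial ANOVA establishes safety. The clinical safety triggers and the monitoring committee's review do not depend on it either. This is worth correcting, but it concerns secondary endpoints.

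**What to change.** Name one prespecified analysis for serial urinary NGAL: a linear mixed model on log NGAL with arm, time and arm x time, using all available samples. Report the Low/High geometric mean ratio with a confidence interval at each time. Treat other serial markers the same way only if they prove right-skewed. Repeated-measures ANOVA then need not be the first choice.

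The cost is a sentence or two in the protocol or analysis plan. No extra data, samples or participants are needed, and the software is standard. The one small drawback is that results appear as ratios rather than differences in ng/ml.

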The current practice of maintaining a high UO in otherwise well patients by liberal fluid infusions can be therefore be questioned. More importantly, a series of recent randomised clinical trials demonstrate that liberal fluid therapy approximately doubles postoperative complication rates as compared to a more restricted fluid regime, confirming findings in animal studies of numerous detrimental effects of perioperative fluid overloading. Three clinical trials demonstrate a relative reduction of 46%, 45% and 84% of overall postoperative morbidity with restricted fluid therapy, clearly identifying fluid overloading as a major, iatrogenic and preventable cause of complications in contemporary surgical care. The main obstacle to fluid restriction in practice is maintaining the traditional high UO target. This study therefore aims to demonstrate that a lower UO target is not associated with renal impairment, confirming previous observational studies.

Aims

This study tests the hypothesis that a urine output target lower than the traditional 0.5 ml/kg/h (0.2 ml/kg/h) does not cause harm to the kidneys. Harm is defined in the widest sense of the word in order to detect any degree of harm. It is therefore evaluated by several highly sensitive methodologies beyond the routinely used serum concentrations of creatinine and urea. These methods include frequent sampling for novel, validated biomarkers of renal stress (neutrophil gelatinase-associated lipocalin (NGAL) and Cystatin C) in combination with renal clearance studies to directly measure renal plasma flow (para-aminohippurate (PAH) clearance) and glomerular filtration rates (Sinistrin clearance).

Importance

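### Post-hoc Tukey is a poor fit for comparing Low with High over time on the secondary serial markers; same-time contrasts from the already permitted mixed model should replace it

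*Protocol*

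**What the plan says.** The last part of Statistical considerations assigns repeated measures to an analysis of variance, "time x treatment group with post-hoc Tukey's test as appropriate", "or mixed regression models if appropriate". The next sentence adds simple two-group tests: "Student's unpaired t-test or, if non-normally distributed, Mann-Whitney U test and Fisher's exact test will be used as appropriate". No comparison family and no error term are named for the Tukey step.

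The data concerned are the serial secondary markers in Table 3: urinary NGAL, creatinine and osmolality, and plasma cystatin C, creatinine, osmolality and hormones. Under Study design, NGAL "will be followed 12-hourly during 48 hours", and the other renal measures "will be measured several times per day". Under Endpoints, urine and plasma are taken "at regular intervals during and 72 hours after surgery and once on POD 30", in addition to the preoperative visit.

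The primary endpoint is a single time: "The primary endpoint is urinary concentration of NGAL at 2 pm on POD 1". Under Aims, the protocol sets a demanding standard for the safety evidence as a whole: "Harm is defined in the widest sense of the word in order to detect any degree of harm".

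**The concern.** For these markers the question is whether Low is worse than High at a given time. Tukey's procedure controls error over all pairwise differences among a set of means. A two-level arm effect needs no such procedure, and Tukey on the time effect compares no arms. So the named step bears on the trial's question only if it runs over every arm-by-time cell. Most of those pairs set one time against another, where surgery itself is expected to cause change. Standard Tukey also assumes independent cells with one error variance, which serial samples from the same patient do not satisfy.

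The stake is how much weight the supporting safety results can carry. A needlessly large critical value makes a real difference between arms easier to miss, in a trial that hopes to show none. If software instead applies the ANOVA's within-subject residual, the standard error of a between-patient comparison omits between-patient variance, and the fault runs the other way.

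**Working it through.** **The plan's own figure.** Inputs from Statistical considerations: margin 15 ng/ml, SD 15 ng/ml, one-sided alpha 0.05, power 90%, dropout 10%.
- n per arm = 2 × (1.645 + 1.282)² × (15/15)² = 17.1, rounded up to 18; 18/0.9 = 20 recruited.
- Noncentral-t power at 18 per arm is 90.2%. The stated size reproduces.

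**Assumptions for the serial markers.** 18 completers per arm; a true difference of 1 SD (15 ng/ml with SD 15) at one time; two-sided 0.05 for post-hoc tests. T, the number of times, is not stated. Sampling every 12 h over 48 h suggests T = 5 for NGAL (0, 12, 24, 36, 48 h). Adding the preoperative and POD 30 samples would give 7, and other markers may have more.

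**Size of the family.** There are 2T cells and T(2T − 1) pairs, of which T are same-time arm contrasts. At T = 5 that is 45 pairs, 5 relevant and 40 not; at T = 6, 66 pairs and 6 relevant.

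**Power with the pooled cell variance.** The noncentrality is 1 × √(18/2) = 3. The critical values for |t| are:
- unadjusted: 2.03 (34 df);
- Bonferroni over the T same-time contrasts: 2.73 at T = 5 and 2.80 at T = 6 (34 df);
- Tukey over all cells: q(0.95; 2T, 34T df)/√2 = 3.21 at T = 5 (170 df) and 3.31 at T = 6 (204 df).

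| T | Pairs | Unadjusted | Bonferroni, same-time | Tukey, all cells |
|---|---|---|---|---|
| 2 | 6 | 83% | 74% | 64% |
| 4 | 28 | 83% | 64% | 47% |
| 5 | 45 | 83% | 61% | 42% |
| 6 | 66 | 83% | 58% | 38% |
| 8 | 120 | 83% | 54% | 33% |
| 10 | 190 | 83% | 51% | 29% |

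At T = 5 the step from 83% to 61% is the price of controlling error over five contrasts. The further step from 61% to 42%, 19 points, is due to the wider family. In simulation, the chance of any false arm difference under Tukey at T = 5 is below 1%, far under the nominal 5%.

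**If the within-subject residual is used.** With within-patient correlation ρ (compound symmetry), that residual estimates (1 − ρ)σ², while the arm difference at one time has variance 2σ²/n. The t ratio is inflated by 1/√(1 − ρ), so the false-positive rate per time is about 2[1 − Φ(c√(1 − ρ))]. At T = 5, c = 3.22 (136 df); for ρ = 0.5 this is 2[1 − Φ(2.27)] ≈ 2.3%. Simulated chance of at least one false arm difference over the 5 times:
- ρ = 0.3: about 4%;
- ρ = 0.5: about 9%;
- ρ = 0.7: about 22 to 23%.

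The 5% level is crossed between ρ = 0.3 and 0.4.

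**The case against.** The strongest reply is that the protocol does not commit to this procedure. The Tukey step is conditional, a mixed model is offered in the same sentence, and neither the comparison family nor the error term is stated; a statistical analysis plan could settle both. That stands as a limit on certainty. It does not remove the point, because the step is named, and with two arms the all-cells family is the only reading under which it compares Low with High at a given time.

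Three further replies also stand in part.
- Setting 83% against 42% is not like for like, since the first figure has no multiplicity control. The fair comparison is 61% against 42%.
- The ANOVA also gives an arm effect and an arm-by-time interaction, neither of which needs Tukey. The figures above concern only a difference confined to one time.
- Creatinine safety is also covered by the nephrologist review triggers, the monitoring committee and the halt rule, none of which depends on this test.

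A reader might infer that the serial markers lose most of their power. At T = 5 the loss against an unadjusted test is about half; it exceeds half only from T = 6, and T is not given. A reader might also infer that the standard errors are wrong whichever error term is used. With the pooled cell variance, the standard error of a same-time comparison between different patients is sound, and only the multiplier is too large. The two faults are alternatives: at high correlation with the within-subject residual, power is high (89% at ρ = 0.7 and T = 5) and false positives are the problem.

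**Conclusion.** The point holds as a poorly chosen post-hoc method for secondary endpoints. Used over all arm-by-time cells with pooled variance, Tukey costs about 20 points of power for a 1-SD difference at one time, compared with an adjustment limited to the relevant contrasts (61% to 42% at 5 times, 58% to 38% at 6). With the within-subject residual it can instead raise the familywise false-positive rate to about 9% at ρ = 0.5 and 22 to 23% at ρ = 0.7, with no inflation at 0.3. These sizes rest on 18 per arm, an assumed number of times, an assumed error term and, for the second branch, an assumed correlation. The documents do not support extending the point to the main result: the primary endpoint is one time, lies outside any Tukey family, and its sample size reproduces.

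**What to change.** Delete the Tukey step from Statistical considerations. Make the mixed model that the sentence already allows the stated analysis for the serial markers, with terms for arm, time, arm-by-time and baseline value and a structure for within-patient correlation. Report the Low-minus-High contrast with its confidence interval at each post-randomisation time. If multiplicity is to be controlled, limit the adjustment to those same-time contrasts. Whether to adjust at all, and whether one-sided bounds suit markers with no defined harmful direction such as the hormones and osmolality, can be left to the sponsor.

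The cost is one sentence of analysis text and no new data. Cross-time pairwise tests would no longer be produced, and the narrower adjustment would let through slightly more isolated signals than Tukey with pooled variance.

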Approximately 45% of people in the industrialised world have abdominal surgery during their lifetime. Despite recent significant advances, such as minimally invasive surgery and enhanced-recovery protocols, people undergoing colorectal surgery still have a 35-55% risk of complications. As summarised above, recent trials have identified fluid overloading as a major, iatrogenic and preventable cause of complications in contemporary surgical care. The main cause of fluid overloading is the traditional emphasis on maintaining a high UO. This trial challenges this tradition by evaluating the non-inferiority of a lower UO target, with the ultimate goal of reducing the need for routine aggressive fluid resuscitation in elective surgery and the excess morbidity associated with such fluid excess. The potential impact on the practice and outcomes of surgery across most specialties is therefore large. In addition, this study will elucidate the regulators of renal function in contemporary surgical care, specifically evaluating the respective roles of renal perfusion changes vs changes in renoregulatory hormones.

Table 1. Standardised fluid therapy in ERAS protocol		
Day of surgery	Preop	≥400 ml clear liquids PO Oral bowel preparation not routinely used
	Intraop	5 ml/kg/h Plasma-Lyte 148 IV
		5 ml/kg/h Gelofusine IV
	Postop	0.5 ml/kg/h dextrose-saline IV
		600 ml liquids PO
Total	Approx 2500 ml IV + 1000 ml PO	
POD 1		IV fluids stopped at 8 am
		1500 ml liquids (and standard diet) PO
		If oral intake <800 ml by 6 pm, maintenance infusion of IV dextrose-saline with 20 mmol K/l restarted at 1 ml/kg/h
		In case of vomiting, replacement 1:1 with IV saline 0.9% with 20 mmol K/l is started
		If Hgb <80: Transfuse 2U RBCs If Hgb 80-100: Transfuse 2U RBCs only if symptomatic or ischaemic heart disease or evidence of ongoing bleeding

Study design

This is a prospective randomised assessor-blinded non-inferiority trial. Forty patients undergoing elective bowel surgery will be studied.

Patients with known risk factors for AKI will be excluded.

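### The analysis paragraph does not carry the 15 ng/ml margin and one-sided 0.05 level into the primary NGAL analysis, and its Mann-Whitney fallback, as stated, does not address a mean-difference margin

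*Protocol*

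**What the plan says.** The Study design section is explicit: "This is a prospective randomised assessor-blinded non-inferiority trial". The Aims section frames the hypothesis as showing that the lower urine output target "does not cause harm to the kidneys". The Endpoints section fixes a single time point: "The primary endpoint is urinary concentration of NGAL at 2 pm on POD 1".

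The first part of Statistical considerations is written for that question. The High group is assumed to have mean (SD) 10 (10) ng/ml, the cut-off in the Low group is 25 ng/ml, and the margin is the difference, 15 ng/ml. The calculation uses "a common SD of 15 ng/ml, and 0.05 one-sided significance level" and concludes: "To show non-inferiority with 90% power, a minimum of 18 participants completing the study per treatment group will be needed". The protocol then adds: "Certain data indicate that urinary NGAL follows a log-normal distribution". It gives a second, log-scale calculation, also one-sided at 0.05, with a margin written as log 15 ng/ml.

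The analysis paragraph follows. It names repeated-measures analysis of variance with Tukey's test, or mixed models, for repeated measures, and then: "Student's unpaired t-test or, if non-normally distributed, Mann-Whitney U test and Fisher's exact test will be used as appropriate". It mentions no margin, one-sided limit, log transformation or primary endpoint.

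**The concern.** The sample size assumes a test that rejects a Low-minus-High excess of 15 ng/ml. As ordinarily run, the named methods test whether the excess is zero. These are different questions, and failing to find a difference in 40 patients does not show that a difference of 15 has been excluded.

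The primary endpoint is one continuous value per patient, so the sentence on the t-test and Mann-Whitney is the one that most naturally applies to it. A t-test converts easily to a margin test by shifting the null to 15. The fallback is harder. It is triggered by non-normality, which the protocol expects, and a Mann-Whitney p-value alone carries no quantity in ng/ml to compare with 15. The log-scale margin does not fill the gap. Read literally, log 15 is a 15-fold ratio, whereas 25 against 10 implies 2.5-fold, and the analysis text never says that NGAL will be analysed on the log scale.

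At stake is the error that matters most in a safety trial: reassurance that the data do not support.

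**Working it through.** **Inputs from the protocol.** Margin 15 ng/ml, common SD 15 ng/ml, one-sided alpha 0.05, power 90%, 18 completers per arm (20 recruited), High mean 10, Low cut-off 25.

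**1. The plan's own figure.** n per arm = 2 × (1.645 + 1.282)² × (15/15)² = 17.1, rounded up to 18. The noncentral-t calculation also gives 18. With 10% dropout, 18/0.9 = 20. The sample size therefore reproduces exactly as a margin test. Its power at no true difference is 90.2% with 18 per arm.

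**2. Where the two rules part (n = 18, SD 15).** Standard error = 15 × √(2/18) = 5.0 ng/ml, 34 degrees of freedom.
- Margin test: accept if observed difference + 1.691 × 5.0 < 15, that is, below about 6.5 ng/ml.
- Two-sided 0.05 difference test: non-significant up to 2.032 × 5.0 = about 10.2 ng/ml.

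An observed excess between 6.5 and 10.2 ng/ml is non-significant yet fails non-inferiority.

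**3. Chance that a true excess of 15 ng/ml passes, if non-significance were taken as no harm.** Noncentrality = 15/5.0 = 3.0.

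| Rule | 18 per arm | 20 per arm |
|---|---|---|
| Two-sided 0.05 t-test non-significant | 17.0% | 13.1% |
| One-sided 0.05 t-test non-significant | 9.8% | 7.2% |
| One-sided 95% limit below 15 | 5% | 5% |

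**4. Log-normal NGAL (simulation, 18 per arm, means 10 and 25).** The result depends on how the spread in the Low arm is set, which the protocol does not fix for this case. A CV of 1.0 matches its 10 (10), and 1.5 matches SD 15 over mean 10.

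| Assumed spread | Two-sided Mann-Whitney non-significant | Raw t limit falsely below 15 |
|---|---|---|
| Equal CV 1.0 (SDs 10 and 25) | 12–13% across runs | 11–12% |
| Equal CV 1.5 (SDs 15 and 37.5) | 34% | 14–15% |
| Common SD 15 | about 1% | about 4% |

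Under equal CVs, a log-scale limit against a ratio of 2.5 keeps its 5% in both cases.

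**5. Power of a log-scale margin test at ratio 2.5, no true difference, 18 per arm.** Log SD = √ln(1 + CV²).
- CV 1.0: 0.833; standard error 0.833 × √(2/18) = 0.278; noncentrality ln 2.5/0.278 = 0.916/0.278 = 3.30; power about 94%.
- CV 1.5: 1.086; standard error 0.362; noncentrality 2.53; power about 80% (84% with 20 per arm).

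**The case against.** The other side has several good points.

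- **No stated misreading.** A reader might infer that the protocol will treat a non-significant p-value as proof of no harm, or that the trial as written cannot conclude non-inferiority. The document supports neither. It names the design, the margin, the direction and the alpha, and an unpaired t-test can be run against a null of 15.
- **A generic list.** The sentence includes Fisher's exact test, which cannot apply to a continuous NGAL value, and it stands beside analysis of variance and mixed models. It may be meant mainly for the secondary endpoints.
- **Rank tests can serve.** Mann-Whitney can be inverted to a shift with a confidence limit, or run on rescaled data. Applied to Low divided by 2.5 against High at one-sided 0.05, it falsely accepts in 4.5% (CV 1.0) and 5.1% (CV 1.5).
- **Assumption-driven magnitudes.** The larger log-normal figures come from letting the Low SD grow with its mean. With the protocol's common SD of 15 they nearly vanish.
- **An unseen SAP** may hold the decision rule.

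All of this limits the size and wording of the point. What remains is that the protocol names a fallback, expects the condition that triggers it, and does not say how it would meet the margin. An SAP would have to settle the scale and redirect that fallback, not merely add detail.

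**Conclusion.** The point holds as a mismatch between the design and the stated analysis. The margin and one-sided level appear only in the sample-size text, and the named methods, as ordinarily used, do not test the margin. The sample size itself is sound for the raw-scale margin test.

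The firmest measure of the risk uses the protocol's own inputs: 17% (two-sided) or 10% (one-sided) false acceptance at a true excess of 15 ng/ml, against 5%. Both figures are conditional on a zero-difference test being read as the non-inferiority verdict, which the protocol nowhere says. The Mann-Whitney range, from about 1% to 34%, rests on the assumed spread and should be quoted only with that assumption. It is no ground for saying that a rank test or a raw-scale limit must fail here. Because the primary conclusion depends on the rule, it should be fixed before outcome data are seen by group.

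**What to change.** - Name one primary analysis of urinary NGAL at the primary time point, Low versus High. Declare non-inferiority only if the one-sided 95% upper confidence limit is below the pre-stated margin.
- Choose the scale in advance: a raw difference against 15 ng/ml or, if NGAL is log-transformed, a geometric mean ratio against a margin that the sponsor confirms. The ratio 25/10 = 2.5 follows from the sample-size text, but must be reconciled with the margin of log 15 ng/ml in the log-scale calculation. It equals the ratio of geometric means only if the CVs are equal.
- If a rank method is kept for the primary endpoint, state the shift or ratio estimate and the confidence limit to be compared with the margin.
- Keep zero-difference t, Mann-Whitney and Fisher tests for secondary endpoints, and say that non-significance is not evidence of non-inferiority.

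**Cost.** The text is a few sentences and needs no new data. On the raw scale, 18 completers and 20 recruited per arm stay as they are. On the log scale the margin is a real design decision. At ratio 2.5 with 18 per arm, power is about 94% at CV 1.0 but about 80% at CV 1.5, below the planned 90%, and that should be disclosed.
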